11.1.1 Definitions (investigational device)

11.1.1.1 Adverse device effect (investigational device)

An ADE is an AE related to the use of an investigational device. An ADE must meet 1 or more of the following criteria:

- Adverse event resulting from insufficiencies or inadequacies in the IFU, the deployment, the implantation, the installation, the operation, or any malfunction of the investigational medical device.

- Adverse event that is a result of a use error or intentional misuse of the investigational device.

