14.3.1 Analysis of the primary outcome variable

The primary outcome variable is the percentage of all subjects able to self-administer safe and effective injections using the given device at DV0002 Week 8 (8 weeks after training). Safe and effective self-injection will be evaluated by the study personnel as defined in Section 4.1.1.

The number and percentage of subjects with safe and effective self-injections will be tabulated separately for each device overall and within each device by dosing regimen using the relevant FAS population (FAS-s or FAS-a). The 90% CIs based on the Exact Binomial method will be reported as well.

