### 2.2 Study variables

#### 2.2.1 Primary outcome variable

The primary outcome variable is the percentage of subjects able to self-administer safe and effective injections using the 1mL bimekizumab safety syringe (bimekizumab-SS-1mL), 1mL bimekizumab auto-injector (bimekizumab-AI-1mL), 2mL bimekizumab safety syringe

(bimekizumab SS 2mL), or 2mL bimekizumab auto-injector (bimekizumab-AI-2mL), 8 weeks after training in self-injection technique. Safe and effective self-injection will be evaluated by the study personnel and is defined as:

- Complete dose delivery: Subject self-injects the complete dose of bimekizumab as confirmed by a visual inspection of the device which shows that the investigational medicinal product (IMP) is delivered completely (ie, container is empty), and
- No adverse device effects (ADEs) that would preclude continued use of the device for self-injection (ie, no serious adverse device effects (SADEs) and/or ADEs leading to withdrawal from the DV0002 substudy).

In the DV0002 substudy, for the 1mL devices the 320mg bimekizumab dose will be administered as two 160mg injections with either 2 bimekizumab-SS-1mL devices or 2 bimekizumab-AI-1mL devices. Each self-injection will be evaluated for safety and effectiveness by study personnel using the above criteria. The endpoint of safe and effective self-injection will be met only if both self-injections are determined to be safe and effective.

For the 2ml devices, the 320mg bimekizumab dose will be administered as 1 injection with either 1 bimekizumab-SS-2mL or 1 bimekizumab-AI-2mL device. Each self-injection will be evaluated for safety and effectiveness by study personnel using the above criteria. The endpoint of safe and effective self-injection will be met if the single self-injection is determined to be safe and effective.

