### **2.2.2 Secondary outcome variable**

The secondary outcome variable is the percentage of subjects able to self-administer safe and effective injections using the bimekizumab-SS-1mL, bimekizumab-AI-1mL bimekizumab SS 2mL, or 1 bimekizumab-AI-2mL at DV0002 Baseline (the first self-injection visit, immediately after training in self-injection technique). Safe and effective self-injection will be evaluated by study personnel and is defined as for the primary outcome variable (see Section 2.2.1).

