### **3.10 Changes to protocol-defined analyses**

Subjects who had important protocol deviations affecting the primary outcome variable, as confirmed during ongoing data cleaning meetings prior to database lock, will be not excluded from the FAS-s or FAS-a.

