### **11.1 Primary outcome**

The primary outcome variable is the percentage of all subjects able to self-administer safe and effective injections using the given device at DV0002 Week 8. Safe and effective self-injection will be evaluated by the study personnel as defined below:

- Complete dose delivery: Subject self-injects the complete dose of bimekizumab as confirmed by a visual inspection of the investigational device which shows that the IMP is delivered completely (ie, container is empty), and
- No ADEs that would preclude continued use of the device for self-injection (ie, no SADEs and/or ADEs leading to withdrawal from the DV0002 substudy).

All data to assess the primary outcome is collected on the subject self-injection of bimekizumab CRF page for DV0002 Week 8. For the number of subjects with safe and effective self-injections simply the cases which indicated “yes” for the question “Did the subject self-inject the complete dose of Bimekizumab” and “no” for the question “Where there any AEs related to use of the investigational device for self-injection” at Week 8 are counted.

For subjects in the 1mL device cohort, two self-injections will be performed at DV0002 Week 8 and the questions will be answered twice. If the answers are different between both self-injections in one visit, then the worst case of both answers will be used for analysis at this visit. Subjects with only one self-injection at one visit will be counted as non-responder. Assessments where the self-injection was not performed by the subject will be not included in any summary statistics.

The number and percentage of subjects with safe and effective self-injections will be tabulated separately for each device overall and within each device by dosing regimen. The 90% CIs based on the Exact Binomial method will be reported as well.

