## 11.2 Secondary outcome

The secondary outcome variable is the percentage of subjects able to self-administer safe and effective injections using the given device at DV0002 Baseline (first self-injection visit). Safe and effective self-injection will be evaluated by the study personnel. The secondary outcome variables will be analyzed in the same manner as the primary outcome variable.

All data to assess the secondary outcome is collected on Subject self-injection of Bimekizumab CRF page for DV0002 Baseline.

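### SAP 11.1 defines a safety failure as a serious or withdrawal-causing device effect but counts any device-related AE as a failure, and the secondary endpoint inherits the conflict

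*SAP*

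**What the plan says.** **Definition.** SAP 11.1 requires complete dose delivery together with this safety condition: "No ADEs that would preclude continued use of the device for self-injection (ie, no SADEs and/or ADEs leading to withdrawal from the DV0002 substudy". Protocol 4.1.1 sets the same condition. SAP 2.2.1 repeats it ("No adverse device effects (ADEs) that would preclude continued use of the device for self-injection", with the same explanation in brackets), and Protocol 14.3.1 ties the analysis to that definition: "Safe and effective self-injection will be evaluated by the study personnel as defined in Section 4.1.1".

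**Counting rule.** The next paragraph of SAP 11.1 says that all data for the primary outcome come from the Week 8 self-injection CRF page. A success is a case with a yes for self-injection of the complete dose and a no for "Where there any AEs related to use of the investigational device for self-injection". In the 1mL cohort the questions are answered for each of two injections, and the worse answer is used.

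**Secondary endpoint.** SAP 2.2.2 says that safe and effective self-injection at Baseline "is defined as for the primary outcome variable (see Section 2.2.1"). SAP 11.2 adds: "The secondary outcome variables will be analyzed in the same manner as the primary outcome variable".

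**Declared changes.** SAP 3.10 names one change to the protocol-defined analyses. It concerns "Subjects who had important protocol deviations affecting the primary outcome variable", who are no longer excluded from the Full Analysis Sets. SAP 3.10.1 covers COVID-19 deviations. Neither mentions the endpoint.

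**The concern.** Protocol 11.1.1.1 states: "An ADE is an AE related to the use of an investigational device". SAP 2.2.3.3 gives the same definition. The CRF question therefore asks about ADEs of any kind, while the endpoint definition fails a subject only for the subset that are serious or lead to withdrawal from the substudy. The two rules classify the same subject differently whenever that subject's only device-related event is non-serious and does not lead to withdrawal.

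DV0002 is an estimation study, so the percentage with its exact 90% CI, per device overall and by dosing regimen, is the main result. If the counting rule is programmed as written, the table headed safe and effective self-injection will report a quantity other than the protocol-defined endpoint whenever such a subject exists. Two programmers working from adjacent paragraphs of one section could also produce different primary results.

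**Working it through.** **1. Classify subjects under each rule.** For a subject with complete dose delivery on every required injection:

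| Device-related event marked on the page | Definition (SAP 11.1, Protocol 4.1.1) | Counting rule (SAP 11.1) |
|---|---|---|
| None | Success | Success |
| Non-serious, no withdrawal from DV0002 | Success | **Failure** |
| Serious, or leading to withdrawal from DV0002 | Failure | Failure |

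Only the middle row differs. For events marked on the page, every counted success is also a defined success, so the count can only lower the reported percentage.

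**2. Look for a reconciling passage.** SAP 11.1 takes all the data from that one CRF page and counts on the two answers alone, which leaves no place for a later filter on seriousness or withdrawal. The worse-of-two rule for the 1mL cohort means that one marked event on either injection fails the subject. SAP 3.10 is silent. No other section of either document limits the CRF question.

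**3. Size.** The plan states no success rate, ADE rate or power figure for this endpoint, so there is no figure to reproduce. The inputs are the planned arm sizes of about 100 (1mL) and about 50 (2mL) from SAP 2.3.6, and the exact binomial 90% CI from SAP 11.1.

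- Shift per affected subject = 100/n points: 100/100 = 1.0; 100/50 = 2.0.
- Exact limits for x successes of n: lower = the 5% quantile of Beta(x, n−x+1); upper = the 95% quantile of Beta(x+1, n−x).
- With x = n, the lower limit is 0.05^(1/n): 0.05^(1/100) = 0.970 and 0.05^(1/50) = 0.942.

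Suppose every subject is a success by the definition, and k of them have only a non-serious, non-withdrawal ADE. The values of k are assumptions.

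| k | n=100: counted % (90% CI) | n=50: counted % (90% CI) |
|---|---|---|
| 0 | 100 (97.0–100) | 100 (94.2–100) |
| 1 | 99.0 (95.3–99.9) | 98.0 (90.9–99.9) |
| 2 | 98.0 (93.8–99.6) | 96.0 (87.9–99.3) |
| 5 | 95.0 (89.8–98.0) | 90.0 (80.1–96.0) |
| 10 | 90.0 (83.6–94.5) | not run |

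**4. Smaller denominators.** SAP 3.1 bases outcome percentages on subjects with observed data unless otherwise specified, so the Week 8 denominator may be below the arm size. The following denominators are assumptions.

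| Assumed n | Shift per subject | k=0 | k=2 |
|---|---|---|---|
| 90 | 1.1 | 100 (96.7–100) | 97.8 (93.2–99.6) |
| 45 | 2.2 | 100 (93.6–100) | 95.6 (86.7–99.2) |
| 25 (a 2mL arm split evenly by regimen) | 4.0 | 100 (88.7–100) | 92.0 (76.9–98.6) |

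The even split is for illustration only: SAP 3.7 says that regimen is assigned by an algorithm using feeder study and PASI90 response.

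**The case against.** The best case on the other side concerns importance. The study tests no hypothesis, is not powered for any endpoint and states no success threshold, so no formal decision turns on the percentage. For events marked on the page the error runs one way and is conservative. SAP 10.2.1 tabulates treatment-emergent ADEs, including the serious ones and those leading to discontinuation, so a reader could see that milder events occurred. If no subject has such an event, the two rules agree.

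All of this is true, and it limits the consequence. It does not make the counted percentage the defined endpoint. The ADE tables do not give the corrected percentage or its interval.

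A second objection is that the CRF page and its completion guidelines are not among the documents, and page instructions could narrow what sites mark. This stands as uncertainty about the practical size. As quoted in the SAP, however, the question asks about any device-related AE.

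A third point qualifies the direction. SAP 10.2.1 says that AEs are recorded on the AE page when they occur. No section says whether the self-injection page is updated for events that emerge after the visit. If it is not, a late SADE or withdrawal-causing ADE could escape the count, which would then be too lenient for that subject. This is conditional and secondary to the contradiction.

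**Conclusion.** The contradiction is in the current text of SAP 11.1, nothing in either document resolves it, and it passes to the secondary endpoint through SAP 2.2.2 and 11.2. It must be corrected because, as written, the counting rule does not calculate the protocol-defined primary endpoint.

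The cost is 1.0 point per affected subject in an arm of 100 and 2.0 points in an arm of 50, and more in regimen subgroups. If 10% of subjects were affected and all were otherwise successes, the lower 90% limit would fall from 97.0% to 83.6% at n=100 and from 94.2% to 80.1% at n=50. These are sensitivity figures under assumed counts and do not forecast the result. That the two rules conflict follows from the text alone and needs no assumption about event rates.

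**What to change.** Choose one rule and state it throughout.

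**Preferred: apply the definition.** In SAP 11.1 and 11.2, derive success as complete dose delivery on every required injection and no device-related AE that was serious or led to withdrawal from DV0002, using AE-page and disposition data. Show any device-related AE, taken from the CRF page, as a separate supportive row. State how an event is attributed to the Baseline or the Week 8 self-injection, so that a qualifying event is not lost between visits or when it comes to light at the safety follow-up call (7 days ±3 after the last dose, Protocol Table 5-3). That attribution should not bring in a 7-day cut-off per visit: Protocol 4.1.1 has none, and the 7 days in SAP 10.2.1 run only from the final self-administration.

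**Alternative: keep the stricter count.** If any device-related AE was meant to fail a subject, declare this in SAP 3.10 as a change from the protocol and align SAP 2.2.1, 2.2.2, 11.1 and 11.2.

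**Cost.** The preferred route needs SAP wording and minor reprogramming; device relatedness and seriousness already feed the tables planned in SAP 10.2.1. One check is needed. Protocol 6.3 lets subjects leave DV0002 and continue in PS0014, so confirm that the data separate the two kinds of withdrawal. The alternative needs wording only.

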### 3 DATA ANALYSIS CONSIDERATIONS

#### 3.1 General presentation of summaries and analyses

Statistical analysis and generation of tables, figures, subject data listings, and statistical output will be performed using SAS Version 9.3 or higher. All tables and listings will use Courier New font size 9.

Descriptive statistics will be displayed to provide an overview of the study results. For continuous variables, descriptive statistics will include number of subjects with available measurements (n), mean, standard deviation (SD), median, minimum, and maximum.

For categorical variables, the number and proportion of subjects, will be presented. In addition, for the primary, secondary and other variables the 90% confidence interval (CI) based on the Exact Binomial, will also be presented. Unless otherwise noted, the denominator for percentages should be based on the number of subjects included in the respective analysis set. Subjects with missing data can generally be accounted for using either of the following approaches:

- For summaries of demographics and Baseline characteristics: summarize percentages based on all subjects in the analysis set and include a “Missing” category (corresponding to subjects with missing data for the variable being summarized) as the last row in the list of categories being summarized.
- For summaries of outcome and safety variables, unless otherwise specified: percentages will be summarized based only on those subjects with observed data for the variable being summarized. As the denominator may be different from the number of subjects in the analysis set being considered, the denominator should be displayed in the table. The general format for displaying this will be “n/NSub (%)”

Percentages will be presented to 1 decimal place. If the percentage is 100 or 0, no decimal will be presented. Typically, the % sign should be presented in the column header, but not with each individual value.

For bimekizumab PK concentrations, summary statistics will include geometric mean, geometric coefficient of variation (CV), 95% confidence intervals for geometric mean, arithmetic mean, SD, median, minimum, and maximum. All summaries of PK variables will be based on the observed values. No imputation will be used.

Decimal places for descriptive statistics will always apply the following rules:

- “n” will be an integer
- Mean, SD, and median will use one additional decimal place compared to the original data

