#### Imputation of Partial Stop Dates

- If only the month and year are specified, then use the last day of the month
- If only the year is specified, then use December 31st of that year
- If the stop date is completely unknown, do not impute the stop date.

If the (imputed) stop date is prior to the imputed start date:

- If only the month and year are specified and the month and year of first dose is the same as the month and year of the start date and the stop date is before the date of first dose, then set the start date to the 1st of that month.
- If only the year is specified, and the year of first dose is the same as the year of the start date, and the stop date is before the date of first dose, then use the 1st of January of the year of the start date

Partial start dates for onset date of plaque psoriasis will be imputed as follows:

- If only the month and year are specified, then use the last day of the month.
- If only the year is specified, then use the 31st of December of the year.
- If the start date is completely unknown, do not impute the start date.

In the event of ambiguity or incomplete data which makes it impossible to determine whether a medication was concomitant or an adverse event was treatment emergent, the medication will be considered as concomitant or the adverse event will be considered treatment emergent.

If the intensity of an ADE is unknown, it will be considered as severe.

There will be no special procedures for handling missing data for any other data points.

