## **11 OTHER ANALYSES**

This section contains a detailed description of the analysis of the primary, secondary and other outcome variables. All statistical analyses will be descriptive in nature. No inferential statistical analyses are planned. The analysis is done on FAS-s and FAS-a, respectively.

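### The Week 8 primary denominator is not fixed; on the more specific reading it omits FAS subjects who withdrew after Baseline, including for a device effect, and those injected by someone else

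*SAP*

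**What the plan says.** SAP 11.1 defines the primary outcome as "the percentage of all subjects able to self-administer safe and effective injections using the given device at DV0002 Week 8". Success needs an empty container and no ADE that would rule out further use of the device, meaning no serious ADE (SADE) and no ADE leading to withdrawal from DV0002.

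The data come only from the Week 8 self-injection CRF page. A success is a yes to complete dose and a no to "Where there any AEs related to use of the investigational device for self-injection". Two further rules follow. For the 1mL cohort: "Subjects with only one self-injection at one visit will be counted as non-responder". Generally: "Assessments where the self-injection was not performed by the subject will be not included in any summary statistics".

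The denominator is addressed in three places.
- SAP 3.1, default sentence: "Unless otherwise noted, the denominator for percentages should be based on the number of subjects included in the respective analysis set".
- SAP 3.1, bullet for outcome and safety variables: "percentages will be summarized based only on those subjects with observed data for the variable being summarized", with the denominator displayed because it may differ from the analysis set.
- SAP 11: "The analysis is done on FAS-s and FAS-a, respectively".

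Under SAP 3.6.1.3 and 3.6.2.3, one self-injected and assessed dose is enough to enter the FAS, so the Baseline injection suffices. SAP 4.2 deals with dates and ADE intensity and then says: "There will be no special procedures for handling missing data for any other data points". Protocol 14.2 and 14.8 likewise provide no imputation and no missing-data procedure for this outcome.

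**The concern.** The primary objective is ability to self-inject 8 weeks after training. A subject who stops because of a device effect, or who attends Week 8 but has someone else inject, bears directly on that ability. Protocol 6.3 describes those who leave DV0002 but stay in PS0014 as having a medical condition or preference that stands in the way of further self-injection, so a missing Week 8 page can itself carry information about the outcome. If such subjects leave both numerator and denominator, the percentage describes those who were still self-injecting at Week 8.

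Estimation is the study's only purpose (protocol 14.2), so the percentage and its 90% exact interval are the primary result. The rule that fixes their denominator should not be left to interpretation.

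**Working it through.** **Who leaves the denominator on the more specific reading**
1. Withdrawn between Baseline and Week 8: in the FAS, no Week 8 page, so no observed value, and out under the SAP 3.1 outcome bullet. The visit mapping in SAP 3.2 does not help, because a withdrawal visit carries no self-injection to assess.
2. Present at Week 8, injected entirely by someone else: the assessment is left out under SAP 11.1, so no observed value remains, and out under SAP 3.1.
3. 1mL subject who gave one of two injections: the other person's assessment is left out, one self-injection remains, and the subject is a non-responder. This subject stays in.

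On the full-FAS reading, subjects in cases 1 and 2 stay in N and are not successes.

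**Size**
The plan gives no expected success rate, dropout rate or precision to reproduce. Inputs: about 100 subjects per 1mL arm and 50 per 2mL arm (SAP 2.3.6); 90% exact binomial interval (SAP 11.1). The number k without a scored Week 8 self-injection is an assumption, shown as a range.

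With x successes among N − k observed, gap = x/(N − k) − x/N = [x/(N − k)] × k/N. If every observed subject succeeds, the gap is k/N: 2 points per subject for N = 50 and 1 point for N = 100.

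| N | k | Observed only (90% CI) | Counted as failures (90% CI) |
|---|---|---|---|
| 50 | 1 | 49/49 = 100% (94.1–100) | 49/50 = 98.0% (90.9–99.9) |
| 50 | 3 | 47/47 = 100% (93.8–100) | 47/50 = 94.0% (85.2–98.3) |
| 50 | 5 | 45/45 = 100% (93.6–100) | 45/50 = 90.0% (80.1–96.0) |
| 100 | 1 | 99/99 = 100% (97.0–100) | 99/100 = 99.0% (95.3–99.9) |
| 100 | 5 | 95/95 = 100% (96.9–100) | 95/100 = 95.0% (89.8–98.0) |

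With two observed failures and k = 2, the gap is slightly smaller: 46/48 − 46/50 = 95.83% − 92.00% = 3.83 points (N = 50); 96/98 − 96/100 = 97.96% − 96.00% = 1.96 points (N = 100).

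**The opposing rule**
The CRF question scores any device-related AE as a failure, while the definition counts only SADEs and ADEs leading to withdrawal. Take N = 50, one subject excluded, one other with a non-serious device AE that did not lead to withdrawal, and the rest successful:
- SAP, observed-case: 48/49 = 97.96%.
- Written definition, excluded subject counted as a failure: 49/50 = 98.00%.
- Denominator corrected, CRF safety rule left alone: 48/50 = 96.0%.

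The two departures nearly cancel (0.04 points). Correcting only the denominator leaves the figure 2.0 points below the definition.

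**What the proposed rule would give**
One ADE withdrawal and one Week 8 visit missed for an unrelated reason, everyone else successful:

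| N | Observed-case | Proposed primary | All-FAS |
|---|---|---|---|
| 50 | 48/48 = 100% (93.9–100) | 48/49 = 98.0% (90.7–99.9) | 48/50 = 96.0% (87.9–99.3) |
| 100 | 98/98 = 100% (97.0–100) | 98/99 = 99.0% (95.3–99.9) | 98/100 = 98.0% (93.8–99.6) |

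**The case against.** Observed-case reporting with a displayed denominator is prespecified and consistent with the protocol's no-imputation text. The study is unpowered and descriptive, with no success threshold. Subjects must be willing to self-inject (protocol 6.1), so few may be affected. These points stand, and they limit the consequence.

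Several stronger readings are tempting, but the documents do not support them.
- *SAP 11.1 expressly removes subjects injected by someone else.* It removes assessments. Whether the subject also leaves the denominator depends on SAP 3.1.
- *The reported percentage will be too high.* The wider CRF safety question lowers it, so the net direction is unknown.
- *The two 1mL rules conflict.* One acts on assessments and the other on subjects. Applied in turn, they give non-responder.
- *The full-FAS result is hidden.* The displayed denominator and the analysis-set counts by device (SAP 5.1) give x and N, from which both the percentage and its exact interval follow. The plan simply does not report them.
- *Device effects leading to withdrawal disappear.* They are listed and tabulated under SAP 10.2.1, and an ADE recorded on the Baseline page counts in the secondary outcome. What is missing is how such a withdrawal before Week 8 is scored in the primary outcome.

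The proposed rule also brings some judgement about discontinuation reasons and scores some subjects as failures whatever the reason another person injected. That is a real cost, and it is why the two bracketing percentages belong beside it.

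**Conclusion.** The concern holds in this form. On the more specific reading of SAP 3.1 with SAP 11.1, subjects whose Week 8 result is missing for reasons tied to the outcome leave the primary denominator, including those withdrawn for an ADE that the endpoint counts as a failure. The full-FAS reading, supported by the default sentence in 3.1, the FAS statement in section 11 and the reference to all subjects in 11.1, is not excluded, and the SAP does not choose.

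The 2-point and 1-point effects per subject assume that the others succeed, at the planned arm sizes. The total depends on a number that the documents do not give. No test or decision threshold is affected; what is at stake is the definition of the primary estimate and its interval. This should be fixed, with medium confidence in its practical size.

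**What to change.** In SAP 11.1:
1. State the primary denominator.
2. Count as non-responders (a) FAS subjects who withdrew before Week 8 because of an ADE or SADE, or because their recorded reason shows that they could not or would not continue self-injecting; and (b) subjects present at Week 8 whose injection was given by someone else.
3. Confirm that a 1mL subject who gave only one of the two injections is a non-responder.
4. Score the safety component by the written definition, using SADEs and ADEs leading to withdrawal from the AE page, or show the result both ways. Make this change together with the denominator change.
5. Leave Week 8 visits missed for other reasons out of the primary denominator and show them by reason.
6. Report the observed-case and all-FAS percentages (missing as non-response) with 90% exact intervals as sensitivity analyses.
7. List the change in SAP 3.10, since it departs from the protocol's no-imputation text.

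The cost is SAP wording, one 3.10 entry and an additional table. Discontinuation reasons are already summarised (SAP 5.1), and the PK rules in SAP 9.1 imply that the person injecting is recorded. COVID-19 reasons are captured under SAP 5.3, although the rationale of SAP Amendment 2 ties that analysis to the 2mL phase, so their availability for the 1mL cohort should be checked. The downsides are a slightly lower headline percentage, some interpretation of discontinuation reasons, and a failure score for some subjects injected by another person for reasons other than inability; the observed-case figure makes that last group visible.
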